Appendix I: Pre-Treatment Questionnaire for subjects

Subject Study Number: _____ (will be 1-5 in the order of enrollment)

1. What is your date of birth? _____ (mm/dd/yyyy)
2. Which one choice best describes your race? (Please choose only one answer)

_____ Black or African American

If Black or African American is checked, is your ethnic background:

_____ African

_____ Caribbean

_____ Other Black or African descent

_____ Mixed race (Black or African American + Other)

3. What is your ethnicity? (PLEASE CHECK ONLY ONE)

Hispanic or Latin origin
 Non-Hispanic or Non-Latin origin
 Unknown

Hair Loss History

4. When did you first notice your hair loss? _____ / _____ (month/year)
5. How many dermatologists did you consult for the hair loss on the crown of scalp before a diagnosis of central centrifugal cicatricial alopecia (CCCA) was made? _____
6. Have you been given any type of medical treatment for your vertex hairline recession?
Yes No

[figure not shown]
If yes, please check all medications that you used for a time period of AT LEAST 3 MONTHS and indicate the effect of each treatment on your hair loss by placing an X in the appropriate box.

Treatment Used	Response			
	Regrowth	Prevented further loss	Did not stop loss	Do not know
 Oral Steroid (e.g. Prednisone)				
 Intralesional (injection into the scalp) steroids				
 Topical steroids (clobetasol, halobetasol, fluocinolone, betamethasone dipropionate, triamcinolone, fluocinonide, mometasone)				
 Hydroxychloroquine (Plaquenil®)				

[figure not shown]
 Methotrexate				
 Mycophenolate (Cellcept®)				
 Cyclosporin (Neoral®, Sandimmune®)				
 Topical imiquimod (Aldara®)				
 Spironolactone (Aldactone®)				
 Finasteride (Propecia®, Proscar®)				
 Dutasteride (Avodart®)				
 Tetracycline antibiotic class (e.g. Tetracycline®, Doxycycline®, Minocycline® etc.)				
 Topical tacrolimus (Protopic®)				
 Pioglitazone (Actos®)				
 Azathioprine (Imuran®)				
 Topical minoxidil (Rogaine®)				
 Hair transplants in area of hair loss				
 Other: _____				

Symptoms

[figure not shown]
9. Please indicate your current level of scalp itch from 0-10 by marking the line on the scale below

10. Please indicate your current level of scalp pain from 0-10 by marking the line on the scale below

12. Please indicate your current level of scalp burning from 0-10 by marking the line on the scale below.

13. Please indicate your current level of scalp bumps from 0-10 by marking the line on the scale below.

14. Would you like to add any other comments?

Date of Questionnaire completion: _____ (mm/dd/yyyy)

Thank you for your time.

[figure not shown]
Appendix II: Treatment and Follow-Up Questionnaire for Subjects

Subject Study Number: _____ (will be 1-5 in the order of enrollment)

[figure not shown]
15. Please indicate the effect Revian Red All LED cap treatment had on your hair loss:

Regrowth Prevented Further Loss Did Not Stop Loss Do Not Know

[figure not shown]
16. Please indicate your current level of scalp itch from 0-10 by marking the line on the scale below

[figure not shown]
17. Please indicate your current level of scalp pain from 0-10 by marking the line on the scale below.

18. Please indicate your current level of scalp burning from 0-10 by marking the line on the scale below.

19. Please indicate your current level of scalp bumps from 0-10 by marking the line on the scale below.

20. Would you like to add any other comments?

Date of Questionnaire completion: _____ (mm/dd/yyyy)
Thank you for your time.

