Standardized photos and trichoscopic photos before starting treatment and every 2 months for x 6 total months will be taken to assess hairline stabilization and potential for regrowth. A baseline photo and completion photo will also be taken with a visio device. This will help determine pigmentation of the present hairs throughout the study.

Prior to study enrollment, all participants will receive a detailed explanation of the purpose of the study and will undergo written informed consent. Clinical history of hair loss and history of prior treatment will be obtained by administering a standardized questionnaire to all subjects. Subjects will also fill out a questionnaire regarding symptoms of their hair loss at each visit. There will be 4 visits total (1 Pre-treatment visit and 3 Follow up visits). In order to be eligible, subjects must be diagnosed clinically and histologically with CCCA. Diagnosis will be made only by a board-certified dermatologist.

Setting

This study will be conducted at the Wake Forest Baptist Health Department of Dermatology, [name].

Subjects selection criteria

• Inclusion Criteria

- Women who are between the age of eighteen years and sixty-five years with a biopsy-proven diagnosis of CCCA Stage II-IV. They also must be on stable treatment without changes (on doxycycline, topical steroids, minoxidil and/or post 8 rounds of intralesional steroids) for at least 3 months.
- Subjects will be recruited from outpatient dermatology clinics at the Wake Forest Baptist Health Department of Dermatology.

• Exclusion Criteria

- Subjects with other forms of hair loss that is not CCCA
- Prior treatment with light source for alopecia
- Males are excluded from this study since the prevalence of CCCA in males is so significantly low that it is difficult to find cases in a clinical setting

• Sample Size

We anticipate enrolling 23 subjects in order to assess the effect of Revian Red All LED cap.

Interventions and Interactions

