Each subject will have a clinical assessment of hair loss by the investigator at the start of the enrollment and every 2 months until the study is completed. Clinical signs and symptoms of CCCA will be documented by administering a standardized questionnaire to all subjects. Subjects will complete the standardized questionnaire regarding symptoms of their hair loss at the start of the enrollment and every 2 months until the study is completed. Standardized camera and dermatoscopic photographs of the scalp will be obtained at the start of the enrollment and every 2 months until the study is completed.

Total Visits (4)

- Visit 1 (Pre-treatment Visit)
- Visit 2 (Follow Up Visit, 2 months after Visit 1)
- Visit 3 (Follow Up Visit, 4 months after Visit 1)
- Visit 4 (Follow Up Visit, 6 months after Visit 1)

Subjects will use the Revian Red All LED cap, once daily for 10 minutes for a total of 6 months. Subjects will also be called every 2 weeks to verbally confirm consistent use of the cap

Outcome Measure(s)

The main outcome measure in this study is hairline stabilization and/or regrowth, as measured by standardized photography, after Revian Red All LED cap treatment. Secondary outcomes include patient assessment of stabilization and hair regrowth and reduction of signs and symptoms, if present.

Analytical Plan

We expect to be able to enroll 23 subjects in this study. Descriptive statistics such as mean, standard deviation, and range for demographics and subject characteristics at baseline will be obtained. Severity and extent of scalp involvement of CCCA will be assessed by two measures. The first measure will be scoring of symptoms obtained from two questionnaires given to subjects (Appendix I and II). One questionnaire will be given before treatment begins, and the second questionnaire will be given at the start of each subsequent follow up visit (visits 2 and 3) and at the follow-up visit (visit 4). Pre and post-treatment photographs will also be assessed to determine if further scalp hairline recession is present and to look for hair regrowth. The estimates obtained from the subjects' and physicians' questionnaires (Appendix III) will help in designing a larger, randomized clinical trial. Given the small number of subjects, this study is not powered to test for statistical significance; the study will provide the estimate of baseline scores as well as an estimate of change in scores from baseline.

Risk and Benefits

Risks

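### Appendix II item 15 asks subjects what the cap did rather than what change they saw, with no neutral no-change answer, so it measures patient-assessed stabilization poorly

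*Combined protocol and SAP*

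**What the plan says.** The Outcome Measure(s) section sets the main outcome: "The main outcome measure in this study is hairline stabilization and/or regrowth, as measured by standardized photography". It then adds: "Secondary outcomes include patient assessment of stabilization and hair regrowth and reduction of signs and symptoms, if present".

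The subject's view of her hair loss is collected in Appendix II, item 15: "Please indicate the effect Revian Red All LED cap treatment had on your hair loss". The answers offered are "Regrowth Prevented Further Loss Did Not Stop Loss Do Not Know". Items 16 to 19 score itch, pain, burning and bumps, and item 20 invites free comments. The schedule in Appendix V places this questionnaire at Visits 2, 3 and 4.

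On background therapy, the Inclusion Criteria state: "They also must be on stable treatment without changes", with the permitted treatments and period given as "on doxycycline, topical steroids, minoxidil and/or post 8 rounds of intralesional steroids) for at least 3 months". Appendix I, item 6, asks about treatments used before the study. For each one used for 3 months or more, the subject is to "indicate the effect of each treatment on your hair loss by placing an X in the appropriate box", on the same four categories as item 15.

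The Analytical Plan describes the study as estimating baseline scores and change, and says that the questionnaire estimates will inform a later randomized trial.

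**The concern.** The stated outcome is the subject's assessment of stabilization and regrowth, which is an observation. Item 15 asks for an attribution. In a single-arm study of women who may already be stable on other treatment, a subject has no good basis for making it. If her hair has not changed, none of the four answers simply says so.

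Because estimation is the declared purpose, the validity of each measure matters more here than power does. A proportion taken from item 15 would mix three things: the observed course, belief about its cause, and willingness to guess. Carried into the planning of a randomized trial as a response rate, it would be hard to interpret and could be too favourable to the cap.

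**Working it through.** **1. Is item 15 the only source?** Appendix II runs from item 15 to item 20 without a gap in numbering, and only item 15 concerns hair loss. The DLQI does not ask about change in hair. Item 15 is therefore the only visible source for this secondary outcome. One caution: Appendix I items 7, 8 and 11 do not appear in the text available, so a baseline question on current hair-loss status cannot be excluded.

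**2. What can each subject answer?** The table sets possible courses against item 15 and against a neutral change question.

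| Observed course | Item 15 | Neutral item |
|---|---|---|
| Hair gained | *Regrowth*, or *Do Not Know* | more |
| No change, already stable before the cap | *Prevented Further Loss*, or *Do Not Know* | the same |
| Loss stopped after starting the cap | *Prevented Further Loss*, or *Do Not Know* | the same |
| Loss continues: slower, as before, or faster | *Did Not Stop Loss*, or *Do Not Know* | less |

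In the second row, one answer credits the cap with stability that was already there, and the other discards the observation. The neutral item records that subject correctly. The second and third rows remain together under either wording.

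**3. Can already-stable women enter?** Yes. The Inclusion Criteria require unchanged treatment for at least 3 months and do not require active progression. That this treatment continues unchanged through the 6 months is a reasonable inference; the protocol does not state it.

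**4. How large could the effect be?** The plan gives no figure to reproduce. As an illustration only, suppose the cap has no effect. The expected number marking *Prevented Further Loss* is then E = n × p × a, where

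- n = 23 (Sample Size);
- p = share stable on background treatment (assumed);
- a = share of those who credit the cap (assumed).

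| p | a = 1 | a = 0.5 | a = 0 |
|---|---|---|---|
| 0.30 | 23 × 0.30 = 6.9 | 3.45 | 0 |
| 0.50 | 23 × 0.50 = 11.5 | 5.75 | 0 |
| 0.70 | 23 × 0.70 = 16.1 | 8.05 | 0 |
| 0.90 | 23 × 0.90 = 20.7 | 10.35 | 0 |

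The result runs from none to about 21 of 23, depending on two quantities that the documents do not give. The table shows that the problem could matter. It does not estimate how much it will.

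**The case against.** A reader might infer that the item makes subjects credit the cap, that worsening cannot be recorded, or that harm would go unseen. The documents support none of these.

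- *Do Not Know* is an accurate answer for a subject who cannot say why she is stable. Miscounting requires her to over-attribute.
- *Did Not Stop Loss* does record continuing loss; only its degree is missing. Photographs are assessed for further recession, clinicians rate signs at all four visits, item 20 takes free text, and adverse events have their own reporting route.

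It can also be said that neutral wording does not cure the underlying confounding. Women stable on background treatment would answer *the same*, and the number counted as stable could even rise as some move out of *Do Not Know*. No section defines a responder from item 15, and the item feeds one secondary outcome of a pilot that disclaims significance testing. Prior-treatment responses from Appendix I could already be tabulated against it.

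All of this stands, and it limits the point. It does not answer the measurement fault. The item collects an opinion about cause where the outcome calls for an observation, and it gives an unchanged subject no neutral answer. Photographs and clinician ratings are not a patient assessment, and free text yields no countable category.

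**Conclusion.** The point holds as a flaw in how one secondary outcome is measured. Item 15 is attributional, has no neutral no-change answer, and does not distinguish degrees of continuing loss. With no comparator and with background treatment at entry, it leads already-stable subjects either to credit the cap or to give an answer that hides their stability.

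The direction of concern is towards an over-favourable reading of *Prevented Further Loss*. The size cannot be fixed from the documents: the counts above rest on an assumed stability rate and an assumed crediting share, and should not be quoted as an estimate of bias. The photographic main outcome does not use this item. A reader might also infer that better wording would reveal the cap's own effect. It would not, because no wording can do that without a control group.

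The change is worth making because it is cheap and makes the item measure the outcome that is named.

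**What to change.** Replace item 15 at Visits 2, 3 and 4 with a neutral change question, for example: *Compared with before you started using the cap, the hair on your crown is: more / the same / less / do not know.*

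- Report every category at each visit, including *less* and *do not know*.
- Describe *the same* as observed stability, not as an effect of the cap.
- Tabulate the answers against the Appendix I item 6 responses. The visible text of item 6 does not distinguish current from past treatments, so this table is descriptive only.
- If an attribution question is wanted, keep it as a separate later item that is not used for the outcome.
- If degree of loss matters for planning the next trial, *less* can be split into slightly and much less; the version above does not grade it.

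**Cost.** One reworded item and a minor amendment. Answers already given on the existing wording cannot be pooled with the new ones and must be tabulated separately, which thins a sample of 23.

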Appendix III: Clinician evaluation of signs.

SIGNS	CLINICIAN EVALUATION (Mild/Moderate/Severe)*
Perifollicular scale	
Hyperpigmentation	
Breakage	
Interfollicular scale	

Erythema	
Loss of follicular openings	
Vellus/Intermediate/Terminal hair shafts ^a	

*Mild – affecting <10% of scalp. Moderate – affecting 10-30% of scalp. Severe – affecting >30% of scalp.

For all signs other than Vellus/Intermediate/Terminal hair shafts (see below).

a. Percentage of types of hair shafts

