IRB00094234

NCT05759338

23MAY2024

Revian LED Cap

Study Title: A Pilot Study of Revian Red All LED cap as a novel treatment for Central Centrifugal Cicatricial Alopecia.

Principal Investigator, Co-investigator(s): [name], [name], [name], DO

Sponsor or funding source: None

Background, Rationale and Context

Significance

Central centrifugal cicatricial alopecia (CCCA) is a form of scarring hair loss that predominately affects middle-aged women of African descent.¹ The etiology remains unknown; however, inflammatory mediated destruction of the hair follicles is involved in the pathogenesis. Clinically, the natural progression of CCCA starts at the crown as roughly circular scarred patches, which evolve into scarred areas increasing in size circumferentially. Characteristically, the scar is often smooth and shiny, and the hair density in the affected area is frequently decreased. The hair remaining in the scarred areas is more brittle and shorter than the hair in unaffected areas. Since CCCA is a scarring disorder, it can cause permanent hair loss, dyesthesia, and psychological distress which can affect overall quality of life. Affected individuals may complain of pruritus, pain, or tenderness.²

The management of CCCA is challenging due to limited current treatments and a lack of randomized controlled trials. Management focuses on behavioral and styling modifications, in addition to symptomatic relief. Any potentially damaging hair care practices such as chemical relaxers, heat application to the scalp, and the use of hardening gels and sprays are discouraged.³ Many commonly used therapies are anti-inflammatory in nature, including intralesional steroids, topical steroids, oral antibiotics and increased frequency of hair washing with antidandruff shampoos.⁴ These treatments not only lead to improvement in pruritus and tenderness, but in some cases result in increased hair density.⁵ Since there is limited investigation done to determine the most effective treatment approach for CCCA subjects, it would be of great benefit to determine if there is any advantage in using one particular anti-inflammatory therapy over others and whether one is more efficacious in relieving symptoms or promoting hair regrowth in follicles that have not yet become scarred.

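### Appendix III grades loss of follicular openings in three bands with an open top, so the form cannot record spread within a band or any spread once the sign is Severe

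*Combined protocol and SAP*

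**What the plan says.** Appendix III asks the clinician to grade each sign by the share of scalp affected: Mild is below 10%, and then "Moderate – affecting 10-30% of scalp. Severe – affecting >30% of scalp". Six signs are graded this way. One of them, "Loss of follicular openings", is the item closest to the extent of scarring. The only item recorded as a number is the hair-shaft mix ("a. Percentage of types of hair shafts"), which does not measure scarred area.

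The Significance section describes the disease as crown patches that "evolve into scarred areas increasing in size circumferentially" and says it can cause permanent hair loss. Entry requires a "biopsy-proven diagnosis of CCCA Stage II-IV"; no staging scale is named and no stage is tied to a percentage of scalp.

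Under Outcome Measure(s), the main outcome is hairline stabilization and/or regrowth read from standardized photographs. Reduction of signs and symptoms is secondary. The flow chart in Appendix V schedules photographs, dermoscopic photographs and a grader survey (which I take to be Appendix III) at all four visits. The Analytical Plan promises estimates of baseline scores and of change from baseline. It also says that estimates from the subject questionnaires and from Appendix III will help design a larger randomized trial.

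**The concern.** The study asks whether loss has been halted, in a disease that progresses by outward growth. For a scarring sign the change of interest is worsening. If the form cannot show worsening, its answer defaults to no change, which is the favourable one. The clinician has to judge a percentage in order to choose a band, and the form then discards it. A percentage not written down at the visit could be approximated later only from photographs for which no reading method is given. What is at stake is the quality of the Appendix III change scores, which are among the planning inputs for the next trial. The point concerns the middle and top of the scale.

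**Working it through.** The documents derive no sample size, power or progression rate, so there is no stated figure to reproduce.

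**Inputs from the documents.** The cut-offs are 10% and 30% of scalp (Appendix III). The bands are therefore 10, 20 and 100 − 30 = 70 percentage points wide. Follow-up is 6 months and planned enrolment is 23 (Design; Sample Size).

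**Ceiling.** Any value above 30% up to 100% is Severe. A subject who starts there has no worse grade, whatever the growth. This needs no assumption beyond the form.

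**Width.** For a roughly circular patch treated as flat, diameter ratio = √(area ratio). To leave the starting band, a patch must reach 10% from Mild or exceed 30% from Moderate:

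| Baseline, % of scalp | Next cut-off | Area ratio | Diameter growth |
|---|---|---|---|
| 5 | 10 | 2.00 | √2.00 − 1 = 41% |
| 9 | 10 | 1.11 | 5% |
| 10 | 30 | 3.00 | √3.00 − 1 = 73% |
| 15 | 30 | 2.00 | 41% |
| 20 | 30 | 1.50 | 22% |
| 25 | 30 | 1.20 | 10% |
| 29 | 30 | 1.03 | 2% |

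The form is insensitive just above a cut-off and sensitive just below one.

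**How many subjects?** This needs a baseline distribution and a growth figure, and the documents give neither. As an illustration only, assume baseline extent is uniform over a range, every subject grows by the same amount, and grading is without error. The share whose grade rises is the length of baseline range from which a cut-off is crossed, divided by the total length. For example, with baseline 1-30% and growth of 5 points, subjects at 5-10% and 25-30% cross: (5 + 5)/29 = 34%. With area ×1.25, those at 8-10% and 24-30% cross: (2 + 6)/29 = 28%.

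| Assumed baseline | +5 points | +10 points | Area ×1.25 | Area ×2 |
|---|---|---|---|---|
| 1-30% | 34% | 66% | 28% | 69% |
| 10-30% | 25% | 50% | 30% | 75% |
| 1-50% | 20% | 39% | 16% | 41% |
| 5-60% | 18% | 27% | 15% | 36% |
| 1-100% | 10% | 19% | 8% | 20% |

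If all 23 subjects spread by 5 points, between 0.101 × 23 = 2.3 and 0.345 × 23 = 7.9 would be expected to change grade. More than half register if few subjects start Severe and growth exceeds about 7 points or ×1.57 (baseline 1-30%), or 10 points or ×1.5 (baseline 10-30%). If the baseline reaches well into Severe, more than half can never register: at most (30 − 5)/55 = 45% for 5-60% and (30 − 1)/99 = 29% for 1-100%.

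**The case against.** The strongest reply is that Appendix III is not the instrument for the main outcome. A subject who starts Severe and spreads could still be seen to progress on the photographs taken at every visit. The sentence "Severity and extent of scalp involvement of CCCA will be assessed by two measures" does not rescue the concern either: the text after it names the subject questionnaires as the first measure, and the only other assessment it describes is the photographs. Appendix III enters as a source of planning estimates and fits most naturally under the secondary outcome on signs. Three-level grading is also a defensible choice in a 23-subject pilot that only estimates. Since no rater-error figure is given, the gain from a visual percentage cannot be quantified.

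Most of this stands, and it confines the point to the form. A reader might infer that the trial cannot detect progression in a subject who starts Severe; the documents do not support that, because of the photographs. The reply does not remove the weakness on the form. The photographs have no stated scale, unit, threshold or reader rule, so Appendix III is the only instrument in the documents that attaches a percentage of scalp to extent. The Analytical Plan also names the questionnaires and Appendix III, not the photographs, as the source of estimates for the larger trial.

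**Conclusion.** The point holds for the Appendix III form. The ceiling above 30% follows from the form alone. The within-band loss is also certain and can be large: area can triple, with diameter up 73% on the flat-circle approximation, between 10% and 30% of scalp. Near a cut-off the loss is small.

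Two stronger readings are tempting and should not be drawn. One is that most subjects would be scored as stable. In the illustration that is true for growth of 5 points or ×1.25 under all five assumed baselines, but it fails for larger growth in a mainly Mild or Moderate group. The documents do not say which case applies, and Stage II-IV entry does not show how many subjects start above 30%. The other is that the larger trial will inherit a progression rate that is too low. The plan promises change scores and no progression rate from this item, so the supportable statement is that change on this sign may understate progression. The matter deserves correction because the remedy is cheap; it does not undermine the main outcome.

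**What to change.** In Appendix III, for each of the six banded signs, record the estimated percentage of scalp affected (0-100%) at Visits 1 to 4, and derive Mild, Moderate or Severe from that number.

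In the Analytical Plan, report change from baseline in percent of scalp with loss of follicular openings as a supportive clinician measure alongside the photographic main outcome. Report it separately from the reversible signs such as scale and erythema, so that improvement in those does not mask spread of scarring.

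The cost is six numbers in place of six ticks per visit, or 6 × 4 = 24 per subject, at examinations already scheduled. The downside is that visual percentages vary somewhat between visits. The banded grades can still be reported, so nothing now planned is lost. The change does not supply the missing reading scale for the photographs, which needs its own remedy.
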